**ID Number: NCT05277389**

**Document Date: 06/07/2024**

## **Study Protocol & Statistical Analysis Plan**

We will conduct a stratified, parallel-group, double-blind, randomized controlled trial of remotely delivered START treatment to individuals with severe-to-moderate stroke (with recruitment focused on individuals with low SES). Subjects and assessors will be blinded to the condition making the experiment double blind. Specifically, subjects will be told that we are exploring a new therapy that uses different sounds to improve therapy. Parallel group design will ensure that subjects in the Control group are unaware that their “sounds” are softer than the START group. Trainers may become aware that a loud sound is present thus unique Assessor will evaluate clinical performance before and after training. Assessor will be a certified and practicing occupational therapist.

Fifty-eight subjects will undergo baseline testing in the laboratory to establish their upper extremity impairment, spasticity, and function as well as their self-reported health-related quality of life. Next, subjects will participate in high-repetition training, 2 hr/day for 3 consecutive days focusing on functional object manipulation (details below). Subjects will either receive training with START or without (Control). Subjects will be re-tested immediately following training as well as one-month post to assess retention. Activity trackers will be deployed before (baseline), during, and after training. Aim 1 will evaluate the ability of START to enhance therapy outcomes by assessing the % change clinical assessment of function, spasticity, impairment, and self-reported quality of life, functional independence, and arm usage. Aim 2 will focus on the capacity of these changes to 1) be retained and 2) impact subject’s self-reported quality of life. *NOTE:* While we are planning in-person baseline, end, and retention testing, in response to covid, we have established remote clinical screening (see Potential Challenges and Solutions).

**Study population and screening:** A diverse set of individuals with stroke-induced upper-extremity paresis will be recruited consistent with the 2010 census results (Non-Hispanic white: 69%, Hispanic: 12.5%, African American: 12.3%, Asian: 3.6%, and American Indian: 0.9%). We will include equal numbers of males/females to further examine possible sex differences in treatment effects. As this proposal is geared at reducing post-stroke disparity in individuals with low SES, we put an emphasis on recruiting in this population (see Retention and Recruitment).

Recruitment will proceed through 1) our multi-site collaborative registry of stroke survivors, 2) Barrow Neurological Institute’s NeuroRehabilitation Clinics, and 3) Banner Medical University Hospital. The PI has used these sources for recruitment of stroke participants for the preliminary data for this project and for K99/R00HD073240.

Based on our recruitment history, we expect to screen ~80 potential participants each year, 50 of whom we expect will fit all of our criteria and participate, with ~15% attrition.

After being recruited, subjects will be first interviewed to determine their eligibility (**Table 1**). If they meet the criteria, they will come to the lab to complete baseline testing.

**Baseline Testing:** Baseline testing will include biometrics, stroke injury information, clinical assessment of impairment, spasticity, and function, and patient health-related quality of life (see below). To confirm the stroke injury, recent and/or admittance MRIs, as well as radiology and neurology reports, will be used to confirm date, location, and type of stroke (e.g. ischemic, hemorrhagic). Biometric data (e.g., height, weight, demographics). Hearing tests will be administered (see inclusion criteria); however, it is

**Table 1: Recruitment Criteria**

**Inclusion Criteria**

- 1) >18 years old
- 2) Capacity to provide informed consent
- 3) Cerebral stroke at least 6 months prior to testing
- 4) Presence of severe-to-moderate upper extremity impairment (UEFM < 42/66)
- 5) Corrected pure tone threshold (octave frequencies 250-4000 Hz) norms for their age and gender **NOTE:** Audiometry data will be collected for all participants by lab personnel trained by an audiologist in a sound-attenuated booth. We expect that ~30% of participants will use hearing aids; we will not exclude these individuals but rather include hearing aid use as a covariate in analyses.

**Exclusion Criteria**

- 6) Severe concurrent medical problems (e.g. uncontrolled cardiorespiratory impairment)
- 7) Acute/painful condition/injury of upper

notable that the START effect has been observed in individuals with hearing loss. We will closely monitor and if needed include hearing capacity in statistical models.

To assess impairment, function, and spasticity stroke participants will complete standard clinical assessments.

- (1) *Impairment*: The Upper-Extremity Fugl-Meyer (FMA-UE) will be used to quantitatively evaluate impairment. The FMA-UE is one of the most commonly utilized measure of impairment both in clinical and research settings. It has excellent interrater and retest reliability. Severe-to-moderate impairment will be defined as <42/66.
- (2) *Function*: The Action Research Arm Test (ARAT) will be used to quantify upper extremity function, coordination, and dexterity during tasks relevant to activities of daily living. Nearly all tasks have excellent internal consistency in addition to excellent test/retest and interrater reliability.
- (3) *Spasticity*: Due to high variability in test/retest and inter/intra-rater reliability, two tests will be administered to assess spasticity of the shoulder (ab/adduction) elbow (flex/extension), wrist (flex/extension), thumb (flex/extension), and hand (all digits – extension): Modified Ashworth (MA) and Modified Tardieu Scale (MTS). While MA is the more commonly administered test, it suffers from moderate/weak interrater reliability. The MTS, which is similar to the Ashworth but makes use of goniometers, has excellent test/retest reliability as well as interrater reliability. The modified Tardieu also includes Passive Range of Motion (PROM) which can be assessed independently.

To assess patient's health-related quality of life, we will administer the following generic preference-based measures (GPMs).

- (1) The Stroke Impact Scale (SIS) is a self-report scale of disability and health-related quality of life. We will use the subdomains of hand function, ADL/IADL, and mobility. These domains have excellent test/retest reliability and excellent (hand function, mobility) or adequate (ADL/IADL) inter/interrater reliability. All tested domains also have excellent internal consistency.
- (2) Modified Rankin (MRS) is a patient reported outcome that categorizes functional independence with reference to pre-stroke activities. It has excellent test/retest and inter/intra-rater reliability.
- (3) Motor Activity Log (MAL) is a semi-structured interview of patient reported arm function. It has excellent test/retest reliability and internal consistency.

**Training protocol:** During the baseline assessment, subjects will be given a training kit (**Fig 2**). The training kit includes: a phone (Pixel 2 - Google, Mountain View, CA; OS: Android 10, Chipset: Qualcomm MSM8998 Snapdragon 835) and headphones (JLab studio - JLab Audio, Carlsbad, CA; Drivers: 40mm neodymium; Frequency: 20Hz-20kHz) with a microphone which acts as a backup for audio recordings. The phone comes with a preloaded, custom-built, app developed using android studio with Java for functionality and Extensible Markup Language for the user interface. It can deliver randomly applied sounds per the specifications below and display recorded files and playback using a media player. The app is controlled remotely by the Trainer/Experimenter using AnyDesk App for Android (AnyDesk Software GmbH, Germany); thus, the phone app is controlled remotely by the experimenter. Subjects or caretakers are only responsible for charging the phone and do not have to perform any other actions to manipulate the phone. Further, this ensures that subjects cannot be exposed to loud, startling sounds unless explicitly delivered by the trainer.

Subjects will receive 3 consecutive days of remote, telehealth sessions via secure video service. Upper extremity therapy for individuals with severe impairment focuses on tasks of functional significance e.g., self-feeding. For consistency across subjects and to allow statistical comparison, we have chosen 3 tasks

related to self-feeding: hand extension, object lifting, and arm extension. For the hand extension task, subjects will be seated in front of an unopened, full, soda can. They will be asked to open their hand to grab the soda can. For object lifting, subjects will be asked to lift the soda can to their mouth. If they cannot grasp the can voluntarily or if it is too heavy, they will be assisted or given a small, light block or no object if necessary. Empty soda cans are often crushed by high hand spasticity in individuals with severe stroke; thus, a rigid object (e.g., block is used). For the arm extension task, a soda can will be placed at 80% arm's length away from the subject's body. Subjects will be asked to attempt to reach the soda can and touch it with their hand (grasp if able).

Practice of these tasks will be modified to be amenable to the START protocol. Specifically, subjects will practice attempting each task following two non-startling (80dB SPL) acoustic cues. The first acoustic cue will indicate "get ready." The second acoustic stimulus will indicate "move". During START training, the "move" cue will be randomly replaced with a startling, acoustic stimulus of ~120dB over 0.04s. To reduce anticipation, which is required for a consistent START response, the startling stimulus will be applied during only 33% of trials. This protocol has been well established for generating the highest percentage of startles. Each of the 5 training days, subjects will practice each task 45 times with 15 trials accompanied by the startling, acoustic stimulus. The Control group subjects will practice each task the same amount of times (45) but none of the trials will include the startling, stimulus.

**End- and Retention- Testing:** The same measures (except biometrics) evaluated during Baseline assessment (FMA-UE, ARAT, MA, MTS, SIS, MRS, MAL) will be collected on the final day of training as well as one-month post training. Finally, a questionnaire about START will be administered asking about ease of use, comfort, adverse side effects (none have ever been reported).

**Analysis for Aim 1: To establish that START can increase functional paretic limb usage, we will perform a randomized controlled trial assessing the impact of START on therapy outcomes.**

We hypothesize that training with START will increase paretic arm function (ARAT), self-reported arm function (MAL), and functional independence (mRS) compared to training without START. To assess this, we will evaluate effects of the treatment (START vs control) on a group of random subjects from a parallel group of stroke patients. The hypothesis expects a positive impact over multiple days of evaluation with respect to the baseline. We do not expect the data to conform to Gaussian norms. Therefore, we will utilize a generalized linear mixed model to identify differences between groups in this longitudinal data set. The *treatment* (START vs. control) and the *day of testing* (pre, post) will be setup as the fixed factors. *Subjects* will be treated as a random factor, nested within treatment. Tukey post-hoc tests will be employed with a p-value <0.05 will be used to indicate significance. Analysis will be conducted using R's lme4 package.

**Analysis for Aim 2: To establish that START generates retainable changes that impact quality of life, we will re-assess upper-extremity function and self-reported quality of life (SIS, MRS).**

We hypothesize that A) START gains will be retained more than Control and B) retention will be associated with higher quality of life measures (e.g., SIS) one-month post-START training. For A, the same analysis as proposed above will be conducted except the *day of testing* will compare post-training to one-month post as the fixed factors. To complete the analysis for B, we will utilize a regression analysis between the change in the functional score and the change in the quality of life for each subject. The choice between a linear and a logistic regression will be determined by the data themselves. Analysis will be conducted in R, using the base R functionality.

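### Baseline FMA-UE is measured on every subject but not used to explain differences in change; an FMA-UE-by-day term costs little and may add precision

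*Combined protocol and SAP*

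**What the plan says.** Baseline Testing lists the measure among the assessments that participants complete: "The Upper-Extremity Fugl-Meyer (FMA-UE) will be used to quantitatively evaluate impairment". Table 1 sets the severity criterion as "Presence of severe-to-moderate upper extremity impairment (UEFM < 42/66", and the listed criteria give no lower limit, so scores from 0 to 41 are eligible. The Training protocol describes what happens when hand function does not allow the standard task: "If they cannot grasp the can voluntarily or if it is too heavy, they will be assisted or given a small, light block". Where needed, the task is done without any object.

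The Aim 1 hypothesis is that "training with START will increase paretic arm function (ARAT), self-reported arm function (MAL), and functional independence (mRS) compared to training without START". Under Analysis for Aim 1 the plan states: "we will utilize a generalized linear mixed model to identify differences between groups in this longitudinal data set". Its fixed factors are treatment and day ("pre, post) will be setup as the fixed factors"), while subject "will be treated as a random factor, nested within treatment". No treatment-by-day term is written, and no distribution or link is named, although the data are not expected to be Gaussian. Analysis for Aim 2 uses the same model for hypothesis A, comparing post-training with one month.

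FMA-UE therefore appears as an eligibility criterion and as an outcome, never as a covariate. The plan does accept covariates in principle: hearing-aid use (Table 1) and, if needed, hearing capacity (Baseline Testing).

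**The concern.** The treatment question is whether START subjects change more than Control subjects. In a pre/post comparison, the noise that matters is the spread of individual change. Eligibility allows a wide range of severity, and inability to grasp alters what a subject practises, so the documents themselves make it plausible that severity is related to how far a subject can move on ARAT, MAL or mRS. If it is, part of that spread could be explained by a score already in hand.

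At stake is precision in a small trial. A chance difference between arms in severity could also carry into change. The random subject effect handles differences in level; it does not handle differences in change.

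**Working it through.** **Inputs from the documents.** Total sample size is 58 ("Fifty-eight subjects will undergo baseline testing in the laboratory to establish their upper extremity impairment, spasticity, and function"). The significance threshold is 0.05. The outcomes, fixed factors and random factor are as quoted above.

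**Assumptions.** Allocation is 1:1 (29 per arm), the test is two-sided, the comparison of change is Gaussian, and unadjusted power is 80%. R² is the share of the remaining variance in change that FMA-UE explains. The documents give none of these; the range taken for R² is 0 to 25%.

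**Step 1: the plan's own figure.** The 58 cannot be reproduced, because no effect size, SD or power accompanies it. By the normal approximation, a standardised difference of 0.74 at 80% power gives 58, but so does 0.80 at 85% power. The figure is neither confirmed nor contradicted, and the 80% starting point below is only a reference.

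**Step 2: which form of adjustment matters.** Linear mixed models were fitted to simulated pre/post data (58 subjects, 100 runs per setting, treatment-by-day term included):

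- Adding FMA-UE as a main effect changed the treatment-by-day estimate by less than 1e-13 and its standard error by less than 0.0001. With complete pre/post pairs, the subject effect already absorbs the level of severity.
- Adding FMA-UE-by-day changed the mean standard error as follows, where r is the correlation of FMA-UE with change:

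| r | R² = r² | SE without | SE with FMA-UE-by-day | Ratio |
|---|---|---|---|---|
| 0 | 0 | 1.029 | 1.038 | 1.009 |
| 0.3 | 0.09 | 1.043 | 1.010 | 0.968 |
| 0.5 | 0.25 | 1.049 | 0.910 | 0.867 |

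**Step 3: power with FMA-UE-by-day.** By the noncentral t distribution with 29 per arm and 56 degrees of freedom, 80% power needs d = 0.749. The unadjusted noncentrality is 0.749 × √(29/2) = 2.85.

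Adjustment has three effects:

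- Residual variance is multiplied by (1 − R²).
- Variance is multiplied by about 1.018, for chance imbalance in the covariate between arms.
- One degree of freedom is lost (56 to 55; critical value 2.004).

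The adjusted noncentrality is 2.85 / √[(1 − R²) × 1.018].

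| R² | Noncentrality | Power |
|---|---|---|
| 0 | 2.83 | 79.3% |
| 2% | 2.85 | 80.1% |
| 5% | 2.90 | 81.3% |
| 10% | 2.98 | 83.3% |
| 20% | 3.16 | 87.4% |
| 25% | 3.26 | 89.3% |

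In this calculation, adjustment breaks even where (1 − R²) × 1.018 = 1, at R² = 1 − 1/1.018, or about 1.8%. At R² = 0 the standard error rises by √1.018 = 1.009, about 1%, which agrees with the simulation.

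**The case against.** The strongest case against is that nothing here is an error. Leaving a prognostic covariate out of a randomised comparison does not bias it and contradicts nothing in the plan. The only harm is lost precision, and its size is wholly assumed. That stands: the documents give no correlation between FMA-UE and change, and near zero correlation the adjustment costs a little.

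Several stronger readings are tempting, but the documents do not support them:

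- **That the precision is free.** It costs a degree of freedom and a small variance penalty.
- **That enrolled subjects span the whole range below 42.** Table 1 describes eligibility; the enrolled distribution is unknown.
- **That ARAT has a floor in severe arms, so that its own baseline cannot stand in for FMA-UE.** The plan describes no such floor. Nor does self-report make FMA-UE more useful for MAL and mRS: if those scores carry little about impairment, impairment may predict little of their change.
- **That imbalance in severity goes uncorrected.** The subject effect removes imbalance in level; only its relation to change remains. The trial is also called stratified without naming a factor. If the factor is severity, imbalance is already limited by design; if not, it is not. The documents do not settle which.
- **That adjustment is automatically free of bias.** This is safe for a linear model. Under a non-linear link, adding a covariate can change the quantity estimated, and the plan names no link.
- **That about 49 subjects will remain.** 58 × 0.85 = 49.3, but the 15% attrition in Study population and screening is attached to expected yearly recruitment. The 58 may already allow for it.

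**Conclusion.** The point holds as a modest improvement. A baseline severity score taken on everyone, in a population with a wide eligible range and a training task that varies with hand function, is left out of the models for change. Under the assumptions above, using it in the FMA-UE-by-day form moves 80% power to between about 79% and 89%. Most of that gain needs FMA-UE to explain 10% or more of the remaining variance in change; at 2% it is negligible.

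The figures carry over only approximately to the non-Gaussian mixed model that the plan intends. They were worked for a single change comparison, and Aim 2A has no separate estimate. The case rests on a small, bounded cost against a possible gain, not on a demonstrated loss. A prior gap belongs to the same edit: the treatment-by-day contrast, whose precision is at issue, is not written into the model.

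**What to change.** In Analysis for Aim 1, and in hypothesis A of Analysis for Aim 2:

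1. Write the treatment-by-day term explicitly and name it as the contrast that tests the hypothesis.
2. Add baseline FMA-UE as a continuous covariate with an FMA-UE-by-day term, for ARAT, MAL and mRS. If an end-score model is used instead, enter FMA-UE beside the outcome's own baseline score. Do not rely on a main effect alone in the pre/post model.
3. State the distribution, link and effect measure for each outcome together with the covariate, so that it is clear what the adjusted effect estimates.
4. Fix all of this before unblinding.

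The cost is a few lines of text and no new data. The downside is one degree of freedom and a standard error about 1% larger if FMA-UE turns out not to predict change.

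### No distribution family is named for mRS, an ordered category, and lme4 has no ordinal model; some of the families left open would give the mRS test almost no power

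*Combined protocol and SAP*

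**What the plan says.** The Aim 1 hypothesis names three outcomes: ARAT, MAL and mRS. The description of the quality-of-life measures says of mRS that it "is a patient reported outcome that categorizes functional independence with reference to pre-stroke activities", so it is a category scale.

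Analysis for Aim 1 gives one method for all three outcomes. Because Gaussian behaviour is not expected, the plan adopts a "generalized linear mixed model to identify differences between groups in this longitudinal data set", with treatment and day of testing (pre, post) as fixed factors, subject as a random factor and a 0.05 significance threshold. The software is fixed: "Analysis will be conducted using R's lme4 package".

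No section gives a family, a link, an ordinal method or a cut-point for mRS. Analysis for Aim 2 reuses the same method for retention (part A), so the gap carries over. On size, the document says "Fifty-eight subjects will undergo baseline testing in the laboratory"; it gives no power calculation, effect size or standard deviation.

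**The concern.** A generalized linear mixed model is not defined until its family and link are chosen, because the family fixes how the variance relates to the mean. The plan's stated reason for using one is that Gaussian models do not fit, so an analyst following it would look for a non-Gaussian family. For an ordered category the natural choice is a cumulative-link model, and the named package does not offer it.

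The families that are on offer behave very differently on mRS. Poisson and binomial families tie the variance to the mean, and an mRS score changes far less within a person than either assumes. The standard error is then too large, and a real difference in one of the three Aim 1 outcomes could be missed. Leaving the family open also means that it could be chosen after the data are seen.

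**Working it through.** **Inputs from the document.** 58 subjects; two parallel arms; pre and post measurements; subject as random effect; threshold 0.05; attrition of about 15%.

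**Assumptions (the document gives no figure).**
- 1:1 allocation, so 29 per arm. Applying the 15% attrition to 58 gives 58 × 0.85 = 49.3, so about 25 per arm was also run.
- Two-sided Wald test of treatment × day.
- mRS coded 0–5, with distribution A = 0/8/27/40/22/3% or B = 2/15/40/30/13/0%.
- Latent within-subject correlation of 0.9 or 0.7.
- START shift of 0, 0.5 or 0.8 latent SD, which is about 0, 0.45 or 0.71 mRS points.

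The plan has no power figure to reproduce.

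**Hand check, Poisson.** The mean mRS under A is 0.08×1 + 0.27×2 + 0.40×3 + 0.22×4 + 0.03×5 = 2.85.
- Model SE of the interaction on the log scale: √(4/(29 × 2.85)) = 0.220.
- Effect of a 0.45-point shift: |ln(2.40/2.85)| = 0.172.
- Expected z = 0.172/0.220 = 0.78, against the 1.96 needed.
- For 80% power the log ratio must be about 0.616, a fall of 2.85 × (1 − e^−0.616) = 1.31 points.

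**Why the SE is too large.** Poisson implies a pre–post change SD of √(2 × 2.85) = 2.39 points per subject. The simulated change-score t-test had 82.8% power at correlation 0.9, which implies a change SD of 0.45/(1.96 + 0.95)/√(2/29) = 0.59. The ratio is 2.39/0.59 = 4.05. At correlation 0.7 (power 53.9%) the implied SD is 0.45/(1.96 + 0.10)/√(2/29) = 0.83, and 2.39/0.83 = 2.9. Both agree with the simulated Poisson SE ratios of 3.98 and 2.85.

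**Hand check, binomial out of 6.** The proportion falls from 2.85/6 = 0.475 to 2.40/6 = 0.40.
- SE on the logit scale: √(4/(29 × 6 × 0.475 × 0.525)) = 0.304.
- Effect: 0.305, so the expected z is about 1.0.
- With simulated SE ratios of 2.98 and 2.11, power is about P(Z > 0.95 × 2.98) = 0.2% and P(Z > 0.95 × 2.11) = 2.2%.

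**Simulation.** 1,000 trials per setting, random-intercept models fitted by Gauss–Hermite maximum likelihood in Python rather than in lme4. The table shows distribution A with 29 per arm. Each pair is correlation 0.9 / 0.7.

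| Model | Model SE ÷ true SE (range over shifts) | Type I error, % | Power at 0.45 points, % | Power at 0.71 points, % |
|---|---|---|---|---|
| Poisson | 3.8–4.1 / 2.7–2.9 | 0.0 / 0.0 | 0.0 / 0.0 | 0.2 / 2.4 |
| Binomial out of 6 | 2.9–3.0 / 2.1 | 0.0 / 0.0 | 0.1 / 2.0 | 14 / 23 |
| Bernoulli, mRS ≤ 2 | not reliable | 0.3 / 2.1 | 14 / 22 | 32 / 47 |
| Gamma, scale estimated | 0.99–1.00 / 1.00–1.02 | 5.7 / 5.3 | 83 / 53 | 99 / 91 |
| Cumulative-logit mixed | see below | 4.6 / 4.9 | 76 / 53 | 95 / 91 |
| Change-score t-test | – | 4.9 / 4.6 | 83 / 54 | 99 / 91 |

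- Bernoulli: 22–27% of fits gave no usable estimate at correlation 0.9.
- Gamma: an mRS of 0 had to be recoded to 1.
- Cumulative-logit: a few extreme estimates at high correlation distort its SE ratio (0.55–0.96 across settings), so its rejection rates are the figures to read.
- Distribution B (correlation 0.9, 0.5 latent SD): Poisson 0.0%, binomial 0.5%, Gamma 80%, ordinal 78%, t-test 85%.
- 25 per arm (A, correlation 0.9, 0.45 points): Poisson and binomial 0.0%, ordinal 70%, t-test 77%.

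A separate simulation (29 per arm, assumed mRS distribution, 0.5 latent SD shift) gave a Poisson SE 2.6–4.1 times the true SE and 0% power. Baseline-adjusted proportional-odds or linear regression had 59–89% on the same data, and a change-score t-test 51–87%.

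**The case against.** The strongest reply is that the plan names neither Poisson nor binomial, so the near-zero power belongs to families that it may never use. That stands: the figures show what the silence permits, not what will happen.

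A reader might infer that every non-Gaussian family in lme4 gives wrong standard errors for mRS. The check does not support this. Gamma with estimated scale had correct standard errors and full power, although it needs positive values and treats the codes as a continuous measure. A Bernoulli model at a prespecified cut is a legitimate likelihood that mainly loses power and stability.

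It can also be said that ordinal software is not essential. With complete pre/post data and a positive subject variance, the change-score t-test is the treatment-by-day test of a random-intercept linear model. lme4 fits that model, and the t-test did as well as the ordinal mixed model or better. This also stands as statistics, but the plan expressly moves away from Gaussian models.

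A reader might infer a risk of false positives. For mRS the Poisson and binomial error goes the other way, with type I error near 0. For ARAT, two simulations under a Poisson family gave type I error from 0.2% to 12% and from 0% to 8% as the assumed change SD went from 3 to 8 points. Neither that family nor those SDs are in the document, and no MAL simulation was run, so this is illustrative only.

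Finally, the lme4 limit is not stated in the document. Without it, the plan still names no distribution for an ordered category.

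**Conclusion.** The concern holds as a specification gap with a demonstrable cost. The plan sets Gaussian models aside and sends an ordered category to a mixed model with no stated family, in a package that cannot fit the natural ordinal model. Under the assumed mRS distributions, correlations and 1:1 allocation, two of the open families inflate the standard error about 2 to 4 times and leave 0–2% power at a 0.45-point shift. Sound analyses of the same kind of data have about 53–89%.

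The size depends on how much mRS varies within subject: the more stable the score, the worse the fixed-dispersion families do. The consequence for mRS is a missed effect. No firm claim is made about ARAT or MAL beyond the fact that their family is also unstated.

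**What to change.** In Analysis for Aim 1, name a model for each outcome.

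- **mRS:** proportional-odds regression of post-training mRS on arm and baseline mRS. A cumulative-logit mixed model (for example `clmm` in R's `ordinal` package) is an alternative. It can give unstable estimates when within-subject correlation is high, so the baseline-adjusted regression is the safer default.
- **ARAT and MAL:** a baseline-adjusted linear model, with robust standard errors or a permutation test to cover non-normality.
- **Aim 2A:** use the same models with the one-month score as outcome, and state which earlier score is the covariate, because the post-training score is itself affected by treatment.

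The cost is SAP wording and, for the ordinal models, R software other than lme4. The downsides are that proportional odds must be checked and that sparse mRS levels may need merging. The merging rule should be written down before unblinding.

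### No planned START-versus-Control contrast tests change from baseline to one month in MAL or mRS, although both are collected at that visit

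*Combined protocol and SAP*

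**What the plan says.** Analysis for Aim 1 hypothesises that START will "increase paretic arm function (ARAT), self-reported arm function (MAL), and functional independence (mRS) compared to training without START". The aim is framed as raising use of the affected limb, and the hypothesis expects benefit on more than one assessment day relative to baseline. The model for this is: "The *treatment* (START vs. control) and the *day of testing* (pre, post) will be setup as the fixed factors".

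On timing, End- and Retention- Testing says that the measures, MRS and MAL included, "will be collected on the final day of training as well as one-month post training". The opening section agrees: "Subjects will be re-tested immediately following training as well as one-month post to assess retention".

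On content, the list of quality-of-life measures says "Modified Rankin (MRS) is a patient reported outcome that categorizes functional independence with reference to pre-stroke activities", and describes MAL as an interview on arm function as the patient reports it. No recall period is given for either.

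For the one-month values, Analysis for Aim 2 has two parts. In part A, "the same analysis as proposed above will be conducted except the *day of testing* will compare post-training to one-month post as the fixed factors". Part B is a "regression analysis between the change in the functional score and the change in the quality of life for each subject"; the interval over which change is taken is not stated.

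**The concern.** Aim 1 makes a claim about use and independence, but its model stops on the last training day, before the patient has lived any day after completing training. ARAT is a performance test and can be judged on the spot. MAL and mRS ask about life outside the session, and the visit at which such a change could have developed is the one-month visit. That visit enters the between-group analysis only through Aim 2A, with baseline left out.

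The natural question for these two outcomes is whether START patients are better off at one month than at baseline, compared with Control. The plan has no test or confidence interval for it. A reader would have to join two results: Aim 1 (did a difference appear by the last day?) and Aim 2A (did the difference change afterwards?). A non-significant Aim 2A result does not show that a gain held.

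**Working it through.** **Schedule against contrasts.**

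| Interval | MAL and mRS collected at both ends? | START-versus-Control contrast written? |
|---|---|---|
| Baseline to last training day | Yes | Yes, Aim 1 |
| Last training day to one month | Yes | Yes, Aim 2A |
| Baseline to one month | Yes | No |

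Time lived after completed training is 0 days at the Aim 1 post visit and about one month at the retention visit. This holds whether training lasts 3 days (opening section, Training protocol) or 5 days (the later sentence on daily trial counts). Those two statements conflict and must be reconciled, because they set the date of post. The Aim 2 heading names SIS and MRS but not MAL, so it is also unclear whether Aim 2A covers MAL.

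**Why the two written contrasts do not supply the third.** On a linear scale, the baseline-to-one-month effect is the Aim 1 effect plus the Aim 2A effect. The two come from separate fits that share the post value with opposite signs. With unit SD, common correlation ρ and the same patients at all visits, each change has variance 2(1−ρ) and the covariance of the two changes is ρ−1. The variance of their sum is 4(1−ρ) + 2(ρ−1) = 2(1−ρ). Adding the two variances without the covariance gives 4(1−ρ), which inflates the standard error by √2. A valid interval needs one joint model.

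**Illustration of what each contrast can see.** The plan gives no effect size, SD or power, so there is no figure of its own to reproduce.
- From the documents: 58 subjects, ~15% attrition, significance at 0.05.
- Assumed: 1:1 allocation (58/2 = 29 per arm), two-sided testing, all attrition between post and one month (29 × 0.85 = 24.65 per arm), normal approximation, equal SDs and equal correlation ρ between visits. The test in each model is taken to be the treatment-by-day interaction, which the plan does not name.

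SD of change: σc = √(2(1−ρ)); at ρ = 0.7, √0.6 = 0.775.

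Power ≈ Φ(δ / (σc √(2/n)) − 1.96).
- n = 29, δ = 0.5: 0.5 / (0.775 × 0.263) = 2.46, so Φ(0.50) = 69%.
- n = 24.65, δ = 0.5: 0.5 / (0.775 × 0.285) = 2.27, so Φ(0.31) = 62%.

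| Effect at post, at one month (SD) | Aim 1 | Aim 2A | Baseline to one month |
|---|---|---|---|
| 0, 0.5 (late) | 5% | 62% | 62% |
| 0.5, 0.5 (held) | 69% | 5% | 62% |
| 0.5, 0.1 (fading) | 69% | 44% | 7% |

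For the held effect, baseline-to-one-month power is 42%, 62% and 98% at ρ = 0.5, 0.7 and 0.9, against 48%, 69% and 99% for Aim 1. Aim 2A stays at 5% throughout, because its true contrast is 0.5 − 0.5 = 0.

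In the fading row, Aim 2A is non-significant in 100 − 44 = 56% of trials. A significant Aim 1 with a non-significant Aim 2A is therefore what one would see for a held gain, and often for a faded one.

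**Cost in precision.** The minimum detectable effect at a single visit with 80% power is (1.96 + 0.84) × √(2/n): 0.74 SD at n = 29 and 0.80 SD at n = 24.65.

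**The case against.** The best defence is that the plan deliberately separates immediate change (Aim 1) from retention (Aim 2), and that together they cover the month. Much of this stands.

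- A reader might infer that an effect emerging after training would be missed. The documents do not support that: Aim 2A keeps treatment as a factor and, in the late scenario, has the same 62% power as the baseline-to-one-month contrast.
- A held effect is not wholly invisible. Treatment is a fixed factor in the Aim 2A model and Tukey comparisons are planned, so a START-versus-Control difference at one month could be extracted, and randomization makes it valid without baseline. But the plan does not say which pairs will be examined. The comparison also loses precision: at 0.5 SD and 24.65 per arm, 0.5 / 0.285 = 1.76 and Φ(−0.20) = 42%, against 62% with baseline at ρ = 0.7. At ρ = 0.5 the two are equal.
- A reader might infer that one-month values are never set against baseline anywhere. That is not established, because Aim 2B leaves its change interval open. Aim 2B is, however, an association across subjects and not a group comparison.
- It is tempting to say that final-day answers mostly describe life before training, and to put a number on the dilution. With 2 days since the first session (3-day schedule) and assumed recall of 7, 14 or 30 days, the share is 29%, 14% or 7%. With 4 days (5-day reading) it is 57%, 29% or 13%. A spread of 7% to 57%, on windows the documents do not give, is not an estimate.
- It is also tempting to put a final-day difference down to expectation. Subjects and assessors are to be blinded, and Control subjects also hear sounds, so the documents give no reason for expectation to differ between arms.

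**Conclusion.** The point holds as a gap in the specified contrasts. The plan collects MAL and mRS at baseline, last training day and one month, and tests the first and second intervals between groups but not the whole. This sits badly with Aim 1's own goal and with its hypothesis of benefit on several days relative to baseline. The structural finding rests only on the schedule and the two model statements.

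The size is illustrative. For a 0.5 SD effect held to one month at ρ = 0.7, the contrast that includes baseline has 62% power, while Aim 2A rejects at its 5% error rate. Effect, correlation, allocation and timing of attrition are assumptions, and the normal approximation is rough for outcomes that the plan expects to be non-Gaussian.

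A reader might go further and conclude that one month should replace the final day as the deciding Aim 1 result for MAL and mRS. The documents do not require that. Separating immediate change from retention is a defensible choice, and the one-month visit is the more exposed to loss.

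**What to change.** In Analysis for Aim 1, fit one mixed model per outcome with three levels of day of testing (pre, post, one-month), including the treatment-by-day interaction explicitly. Pre-specify two START-versus-Control contrasts: pre-to-post, as now, and pre-to-one-month. Report the second beside the first for MAL and mRS. Take the Aim 2A contrast (post to one-month) from the same model, and say that a non-significant result there is not evidence of retention. State which Tukey comparisons will be used. State the recall period used for MAL and mRS, and the interval for change in Aim 2B.

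No visit or measure is added. The cost is one more contrast per outcome, which should be counted in whatever multiplicity rule is adopted, and somewhat lower precision at one month: the single-visit detectable effect moves from 0.74 to 0.80 SD if all of the expected ~15% attrition falls before that visit. The joint model still uses the earlier visits of patients who are lost.
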